6.5.1.2 Dose reduction/interruption due to liver function abnormalities and thrombosis/embolism

Eltrombopag dose may be interrupted when clinically indicated at the discretion of the investigator. Serum ALT, AST and bilirubin (total, direct and indirect) should be measured prior to initiation of eltrombopag, every 2 weeks while adjusting the dose and monthly after establishment of a stable dose. Abnormal serum liver function tests (LFTs) should be evaluated with repeat testing preferably within 48-72 hours (see [Table 6-7](#) and [Section 6.5.2.1](#)). If the abnormalities are confirmed, serum liver tests should be monitored weekly until the abnormalities resolve, stabilize, or return to baseline levels. Alternative causes of LFT elevations, such as hepatitis or concomitant medications (e.g., cyclosporine A) must always be investigated.

NOTE: Eltrombopag is known to cause interference in measurement of total bilirubin, which may lead to falsely increased levels of total bilirubin (see [Section 8.4.1](#)). Please take dose modification decision based on direct (conjugated) bilirubin (DBIL) along with ALT and/or AST (see [Table 6-7](#) below).

[Table 6-7](#) summarizes the recommendations for dose interruption or reduction of eltrombopag in the management of liver function abnormalities and thrombosis/embolism events. For participants who fulfill the criteria of eltrombopag discontinuation in [Table 6-7](#), refer to [Section 9.1](#) for the further action to be taken after discontinuation.

Table 6-7 Guidelines for eltrombopag dose modification based on liver function abnormalities and thrombosis/embolism

Criteria	Action
Isolated AST or ALT elevation	
> ULN - 3 x ULN	Maintain dose level.
> 3 - 5 x ULN	Maintain dose level. Repeat liver function test (LFTs) ^a as soon as possible, preferably within 48-72 hours from awareness of the abnormal results. If abnormal lab values are confirmed upon the repeat test, then monitor LFTs ^a weekly, or more frequently if clinically indicated, until resolved to \leq 3.0 x ULN. Discontinue participant from eltrombopag if elevation is combined with any of the following: 
 • Clinical symptoms of liver injury or evidence for hepatic decompensation • Persistence for \geq 4 weeks
> 5 - 10 x ULN	Interrupt dose.

Criteria	Action
	
Repeat LFTs^a as soon as possible, preferably within 48-72 hours from awareness of the abnormal results. If abnormal lab values are confirmed upon the repeat test, monitor LFTs^a weekly, or more frequently if clinically indicated, until resolved to $\leq 3.0 \times$ ULN, then:
 
If resolved in ≤ 14 days, then resume at same dose level; If toxicity recurs at same dose, then follow the above guideline and resume dose at a lower dose level (decrease by one level^c)
 
If resolved > 14 days and ≤ 28 days, then decrease one dose level^c
 
If not resolved within 28 days, then discontinue participant from study treatment

$> 10 - 20 \times$ ULN	
Interrupt dose.
 
Repeat LFTs^a as soon as possible, preferably within 48-72 hours from awareness of the abnormal results. Monitor LFTs^a weekly, or more frequently if clinically indicated, until resolved to $\leq 3.0 \times$ ULN. If resolved within 28 days, decrease by one dose level.
 
If not resolved to $\leq 3.0 \times$ ULN within 28 days, then discontinue participant from study treatment.

$> 20 \times$ ULN	
Discontinue participant from study treatment.
 
Repeat LFTs^a as soon as possible, preferably within 48-72 hours from awareness of the abnormal results. If abnormal lab values are confirmed upon the repeat test, monitor LFTs^a weekly, or more frequently if clinically indicated until resolved to baseline or stabilization over 4 weeks.

Combined^b elevations of AST or ALT and direct bilirubin (DBIL)	

For participants with normal baseline ALT and AST and DBIL value, [AST or ALT $> 3 \times$ ULN] combined with [DBIL $> 2 \times$ ULN] without evidence of cholestasis
 
OR
 
For participants with elevated baseline ALT or AST or DBIL, [AST or ALT $> 3 \times$ baseline] OR [AST or ALT $> 5 \times$ ULN], whichever is lower, combined with [DBIL $> 2 \times$ baseline AND $> 2 \times$ ULN]
	
Discontinue participant from study treatment
 
Repeat LFTs^a as soon as possible, preferably within 48 hours from awareness of the abnormal results, then weekly or more frequently (if clinically indicated) monitor LFTs^a, or more frequently if clinically indicated, until ALT, AST or DBIL have resolved to baseline or stabilization over 4 weeks.
 
Evaluate the possibility of DILI (Section 6.5.2.1)

Thrombosis/embolism	
Deep vein thrombosis, pulmonary embolus, transient ischemic attack (TIA) or stroke, myocardial infarction at any time while on eltrombopag	
Discontinue participant from eltrombopag.
 
If the platelet level is $> 50 \times 10^9/L$ at the time of thrombosis, treatment with enoxaparin or another appropriate anticoagulant is recommended as clinically indicated until the platelet count drops $< 20 \times 10^9/L$ or a standard 3 to 6 month course of anticoagulation is completed.

^a Core LFTs consists of ALT, AST, GGT (Gamma-glutamyl transferase), total bilirubin (direct and indirect), and alkaline phosphatase (ALP)
 
^b "Combined" is defined DBIL increase to the defined threshold concurrently with ALT/AST increase to the defined threshold. If the bilirubin increase is below the defined threshold, guidance for isolated AST or ALT elevation should be followed
 
^c Dose level: for participants ≥ 12 years old, one dose level is 25mg; for participants < 12 years old, one dose level is 12.5mg.
	

Definition of discontinuation: study treatment is permanently stopped earlier than the protocol-planned duration

An isolated bilirubin elevation is not typical for drug-induced liver injury. Bilirubin can be elevated either as part of a “Hy’s law” constellation with a preceding elevation of ALT/AST, or as part of a cholestatic reaction with simultaneous elevation of other cholestatic parameters (ALP, GGT). Isolated bilirubin elevation can be seen in conjunction with drugs that inhibit bilirubin conjugation or excretion, but both scenarios do not typically represent liver injury. Alternative causes of bilirubin elevation, including bilirubin interference (see [Section 8.4.1](#)) should be ruled out before basing dose modification decisions on bilirubin values alone

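### Table 6-7 makes liver-injury symptoms a stop criterion only at AST/ALT >3–5 × ULN; the >5–10 and >10–20 × ULN rows do not mention them

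*Protocol*

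**What the plan says.** Table 6-7 in Protocol Section 6.5.1.2 sets out dose modification for isolated AST or ALT elevation in bands. In the >3–5 × ULN band the dose is maintained, but the row adds: "Discontinue participant from eltrombopag if elevation is combined with any of the following". Two conditions follow. One is "Clinical symptoms of liver injury or evidence for hepatic decompensation"; the other is persistence for four weeks or longer.

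In the >5–10 × ULN band dosing is interrupted. If the enzymes return to ≤3 × ULN in 14 days or less, the instruction is "then resume at same dose level". Resolution after more than 14 and up to 28 days means one level lower. Beyond that the row reads "If not resolved within 28 days, then discontinue participant from study treatment".

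In the >10–20 × ULN band dosing is also interrupted: "If resolved within 28 days, decrease by one dose level", otherwise discontinue. Above 20 × ULN the participant is discontinued in all cases.

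The note below the table defines discontinuation as a permanent stop. Footnote b sends any participant whose bilirubin rise is below the combined threshold back to the isolated AST/ALT rows. Section 9.1.1 makes meeting a Section 6.5.1 stopping criterion a ground on which study treatment must be discontinued, and adds several general grounds.

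**The concern.** The symptom condition is written once, in the mildest band that has any stop trigger, and not in the next two. A site that follows the table literally would permanently stop a symptomatic participant at 4 × ULN, but would find only a resolution clock for the same symptoms at 8 or 15 × ULN. That is a patient-safety inconsistency inside one table.

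The omission looks unintended. The other trigger in the >3–5 row, persistence, does reappear in both higher rows as the 28-day limit. The protocol also ties restart to symptoms elsewhere: after a confirmed QTcF above 500 msec, Section 6.5.1.1 makes resumption depend on there being no cardiac signs or symptoms. The liver rows have no counterpart.

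There is a smaller reporting consequence. Section 2.8.1 of both SAPs (primary and final analysis) summarizes AEs leading to treatment discontinuation separately from those leading to dose interruption or change. Which summary a liver event enters can therefore depend on the enzyme band in which it was managed.

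**Working it through.** No sample size, error rate or event count is involved. The check sets the rows side by side and applies each to one test participant.

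**Test participant.** Clinical symptoms of liver injury or evidence of decompensation are present. DBIL is below the combined threshold, so footnote b routes the case to the isolated rows. AST/ALT is back to ≤3 × ULN on day 10.

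| AST/ALT band | Immediate action | Symptom clause in the row? | Time limit leading to discontinuation | Outcome as written |
|---|---|---|---|---|
| >3–5 × ULN | Dose maintained | Yes | Persistence of 4 weeks or more (4 × 7 = 28 days) | Permanent stop |
| >5–10 × ULN | Interrupted | No | Not resolved within 28 days | 10 ≤ 14 days: restart, same dose |
| >10–20 × ULN | Interrupted | No | Not resolved to ≤3 × ULN within 28 days | 10 ≤ 28 days: restart, one level lower |
| >20 × ULN | Discontinued | Not needed | Not needed | Permanent stop |

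The sequence is stop, restart at the same dose, restart one level lower, stop.

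**Varying the resolution time.** If resolution comes on day 20, then 14 < 20 ≤ 28 and both middle rows give restart one level lower. If the enzymes have not resolved by day 28, both middle rows give discontinuation and agree with the >3–5 row. The mismatch is therefore confined to symptomatic cases that resolve within 28 days.

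**Does other text carry the symptom trigger upward?**
- The combined-elevation row requires a stop, but only once DBIL crosses its threshold.
- The liver-injury work-up in Section 6.5.2.1 also requires raised DBIL to be triggered.
- Section 9.1.1 points back to the Section 6.5.1 criteria. At >5–20 × ULN there is no symptom criterion for it to pick up.
- The other relevant grounds in Section 9.1.1 are harm to well-being, an unacceptable AE possibly related to eltrombopag, a laboratory abnormality judged to prevent continuing, and a safety risk. None is tied to liver symptoms or to an enzyme band.

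**Related wording.** The >3–5 row stops eltrombopag, while the higher rows say "discontinue participant from study treatment". Section 6.1 defines study treatment as all three drugs, so the scope of the stop also differs between rows.

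**The case against.** The strongest reply is that the middle rows are silent on symptoms and do not order restart in spite of them. A reader might infer that they require restart whatever the symptoms. The text does not say so, and that part of the reply stands.

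Nor does the plan force re-exposure. Section 6.5.1.2 describes Table 6-7 as recommendations and lets the investigator interrupt eltrombopag at discretion. The ban on deviations in Section 6.5.1 covers mandatory interruptions and reductions; it does not forbid a longer hold or a permanent stop. A reader might also infer that decompensation without a large DBIL rise is handled only in these rows. That is wrong, because the general grounds in Section 9.1.1 apply at any enzyme value and can require a stop.

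The default actions differ too. At >3–5 × ULN dosing continues, so that row needs an extra trigger to stop it. Above 5 × ULN dosing is already interrupted for everyone, and restart requires resolution to ≤3 × ULN within 28 days. Without symptoms the table tightens with severity. It is also tempting to say that strictness falls steadily as enzymes rise, but >10–20 × ULN (restart one level lower) is stricter than >5–10 × ULN (same dose).

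Finally, the bands are mutually exclusive, so no single value receives two instructions, and the documents state no principle that the action on symptoms must be monotone in AST/ALT. Both points are correct. What remains is that a condition serious enough to be an explicit permanent-stop criterion in one row is not addressed in the next two, and only investigator judgment fills the gap.

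**Conclusion.** The point holds as an inconsistency between rows. Clinical symptoms of liver injury or hepatic decompensation are an explicit permanent-stop criterion only at >3–5 × ULN. The two rows covering >5 to 20 × ULN give no action for them, so on this trigger both are less strict than the >3–5 × ULN row. The effect is limited to symptomatic participants with DBIL below the combined threshold whose enzymes return to ≤3 × ULN within 28 days.

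This rests on two readings: that the definition of discontinuation below the table applies to the >3–5 row, which names eltrombopag, and that the row is fixed by the value that triggered the action. The table does not say how a symptomatic participant is managed when a value of 8 × ULN falls through 4 × ULN, so sites could differ there.

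The documents give no expected number of cases. The primary endpoint and its analysis are untouched, and the enzyme-threshold summaries in SAP Section 2.8.3 come from laboratory values regardless of dosing action. Enrollment was complete when protocol version 03 was issued. The change should be made, but it does not call the design into question. No view is taken on which clinical action is right.

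**What to change.** Reconcile the >3–5, >5–10 and >10–20 × ULN rows of Table 6-7 with each other and with Section 9.1.1, so that each row states how clinical symptoms of liver injury or hepatic decompensation are handled. The sponsor's hepatic-safety reviewers should decide which action applies in each row. The same edit should settle whether a stop in each row means eltrombopag alone or all study treatment. The cost is wording in one table and its cross-reference in Section 9.1.1, with no new assessments.

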6.5.2 Follow-up for toxicities

Participants whose treatment is interrupted or permanently discontinued due to an AE or clinically significant laboratory value, must be followed up at least once a week (or more frequently if required by institutional practices, or if clinically indicated) for 4 weeks, and subsequently at approximately 4-week intervals, until resolution or stabilization of the event, whichever comes first. Appropriate clinical experts such as ophthalmologist, endocrinologist, dermatologist, psychiatrists etc. should be consulted as deemed necessary.

All participants must be followed up for AEs and serious adverse events (SAEs) for 30 days following the last doses of eltrombopag.

6.5.2.1 Follow-up on potential drug-induced liver injury (DILI) cases

Participants with transaminase increase combined with bilirubin increase may be indicative of potential severe drug-induced liver injury (DILI), and should be considered as clinically important events and assessed appropriately to establish the diagnosis. The required clinical information, as detailed below, should be sought to obtain the medical diagnosis of the most likely cause of the observed laboratory abnormalities.

The threshold for further work-up for potential severe DILI may depend on the participant's baseline AST/ALT and DBIL value; participants meeting any of the following criteria will require further follow-up as outlined below:

- For participants with normal ALT and AST and DBIL value at baseline: AST or ALT $> 3 \times$ ULN combined with DBIL $> 2 \times$ ULN
- For participants with elevated AST or ALT or DBIL value at baseline: [AST or ALT $> 3 \times$ baseline] OR [AST or ALT $> 5 \times$ ULN], whichever is lower, combined with [DBIL $> 2 \times$ baseline AND $> 2 \times$ ULN]

As DILI is essentially a diagnosis of exclusion, other causes of abnormal liver tests should be considered and their role clarified before DILI is assumed as the cause of liver injury. A detailed history, including relevant information such as review of ethanol consumption, concomitant medications (including cyclosporine A), herbal remedies, supplement consumption, history of any pre-existing liver conditions or risk factors, should be collected. Laboratory tests are recommended to include ALT, AST, total bilirubin, direct and indirect bilirubin, GGT, glutamate dehydrogenase, prothrombin time (PT)/INR, alkaline phosphatase, albumin, and creatine kinase. Evaluate status of liver for tumors or vascular occlusion – e.g. using CT, magnetic resonance imaging (MRI), or duplex sonography. Perform relevant

examinations (Ultrasound or MRI, Endoscopic Retrograde Cholangio-Pancreatography (ERCP)) as appropriate, to rule out an extrahepatic cause of cholestasis. Cholestasis is defined as an ALP elevation $> 2 \times$ ULN with R value < 2 in participants. Note: The R value is calculated by dividing the ALT by the ALP, using multiples of the ULN for both values. It denotes whether the relative pattern of ALT and/or ALP elevation is due to cholestatic ($R \leq 2$), hepatocellular ($R \geq 5$), or mixed ($R > 2$ and < 5) liver injury. For children, there are caveats to calculating the R-ratio as normal levels of ALP are higher than in adults with standard ranges varying by developmental age. In clinical situations where it is suspected that ALP elevations are from an extrahepatic source, the GGT can be used if available. GGT may be less specific than ALP as a marker of cholestatic injury, since GGT can also be elevated by enzyme induction or by ethanol consumption. It is more sensitive than ALP for detecting bile duct injury (livertox.nih.gov).

Table 6.8 (below) provides guidance on specific clinical and diagnostic assessments which can be performed to rule out possible alternative causes of observed LFT abnormalities.

Table 6-8 Summary of guidance on specific clinical and diagnostic assessments

Disease	Assessment
Hepatitis A, B, C, E	
 Immunoglobulin M (IgM) anti hepatitis A virus; HBsAg, IgM & immunoglobulin G (IgG) anti-HBc, HBV DNA; anti-HCV, HCV RNA, IgM & IgG anti-hepatitis E virus (HEV), HEV RNA
CMV, HSV, EBV infection	
 IgM & IgG anti-CMV, IgM & IgG anti-HSV; IgM & IgG anti-EBV
Autoimmune hepatitis	
 Antinuclear Antibody & Anti Smooth Muscle Antibody titers, total IgM, IgG, immunoglobulin E, immunoglobulin A
Alcoholic hepatitis	
 Ethanol history, GGT, MCV, CD-transferrin
Nonalcoholic steatohepatitis	
 Ultrasound or MRI
Hypoxic/ischemic hepatopathy	
 Medical history: acute or chronic congestive heart failure, hypotension, hypoxia, hepatic venous occlusion. Ultrasound or MRI.
Biliary tract disease	
 Ultrasound or MRI, ERCP as appropriate.
Wilson disease (if <40 yrs old)	
 Caeruloplasmin
Hemochromatosis	
 Ferritin, transferrin
Alpha-1-antitrypsin deficiency	
 Alpha-1-antitrypsin

Other causes should also be considered based upon participants' medical history (hyperthyroidism / thyrotoxic hepatitis – T3, T4, TSH; cardiovascular disease / ischemic hepatitis – ECG, prior hypotensive episodes; type 1 diabetes / glycogenic hepatitis).

Obtain PK sample to determine exposure to eltrombopag and metabolites.

Following appropriate causality assessments, as outlined above, the causality of the treatment is estimated as "probable" i.e. $>50\%$ likely, if it appears greater than all other possible causes of liver injury combined. The term "treatment-induced" indicates probably caused by the treatment, not by something else, and only such a case can be considered a DILI case and should be reported as an SAE.

All cases confirmed on repeat testing meeting the laboratory criteria defined above, with no other alternative cause for LFT abnormalities identified should be considered as "medically significant", and thus, meet the definition of SAE and should be reported as SAE using the term

“potential treatment-induced liver injury”. All events should be followed up with the outcome clearly documented.

6.6 Additional treatment guidance

6.6.1 Treatment compliance

The investigator must promote compliance by instructing the participant to take the study treatment exactly as prescribed and by stating that compliance is necessary for the participant's safety and the validity of the study. The participant must also be instructed to contact the investigator if he/she is unable for any reason to take the study treatment as prescribed. Compliance will be assessed by the investigator and/or study personnel at each visit using pill counts and information provided by the participant. The actual dose and prescribed dose should be captured in the source document at each visit and eCRF. All study treatment dispensed and returned must be recorded in the Drug Accountability Log.

PK parameters (measures of treatment exposure) will be determined in all participants treated with eltrombopag, as detailed in [Section 8.5.1](#).

6.6.2 Emergency breaking of assigned treatment code

This study is an open-label, single arm study.

6.7 Preparation and dispensation

Each study site will be supplied with eltrombopag in packaging as described in [Section 6.1.1](#).

A unique medication number is printed on the eltrombopag label.

As per the treatment assigned to the participant, investigator staff will select the eltrombopag treatment to dispense to the participant. The eltrombopag has a 2-part label (base plus tear-off label), immediately before dispensing the package to the participant, site personnel will detach the outer part of the label from the package and affix it to the participant's source document.

As per [Section 4.6](#), during a Public Health emergency as declared by Local or Regional authorities i.e. pandemic, epidemic or natural disaster, that limits or prevents on-site study visits, delivery of study treatment directly to a participant's home may be permitted (if allowed by Local or Regional Health Authorities and Ethics Committees as appropriate) in the event the Investigator has decided that an on-site visit by the participant is no longer appropriate or possible, and that it is in the interest of the participant's health to administer the study treatment even without performing an on-site visit. The dispatch of study treatment from the site to the participant's home remains under the accountability of the Investigator. Each shipment/provisioning will be for a maximum of 2-week supply during the first 26 weeks and for a maximum of 1-month supply after Week 26, to ensure study treatment supply until next scheduled visit back on site. In this case, regular phone calls or virtual contacts every 1-2 weeks during the first 26 weeks, regular phone calls and every 2-4 weeks after Week 26, or virtual contacts will occur between the site and the participant for instructional purposes, safety monitoring, investigation of any adverse events, ensuring participants continue to benefit from treatment, and discussion of the participant's health status until the participants can resume visits at the study site.

6.7.1 Handling of study treatment and additional treatment

6.7.1.1 Handling of study treatment

Study treatment must be received by a designated person at the study site, handled and stored safely and properly and kept in a secured location to which only the investigator and designated site personnel have access. Upon receipt, all study treatment must be stored according to the instructions specified on the labels and in the Investigator's Brochure. Clinical supplies are to be dispensed only in accordance with the protocol. Technical complaints are to be reported to the respective Novartis Country Organization (CO) Quality Assurance.

Medication labels will be in the local language and comply with the legal requirements of each country/region. They will include storage conditions for the study treatment but no information about the participant except for the medication number.

The investigator must maintain an accurate record of the shipment and dispensing of study treatment in a drug accountability log. Monitoring of drug accountability will be performed by monitors during site visits or remotely and at the completion of the trial. Participants will be asked to return all unused study treatment and packaging at the end of the study or at the time of discontinuation of study treatment.

At the conclusion of the study, and as appropriate during the course of the study, the investigator will return all unused study treatment, packaging, drug labels, and a copy of the completed drug accountability log to the Novartis monitor or to the Novartis address provided in the investigator folder at each site.

